6.1.2 Patient level subgroups

Owing to the number of children in the study, subgroups defined by child-level factors will have large sample sizes and more power to identify and estimate subgroups and treatment effects within those subgroups using statistical approaches. However, there are far too many patient-level factors to treat as levels to create subgroups. For that reason, we shall implement latent class analysis to group children into subclasses. **Table 6.1b.** Child-level factors for identifying subgroups for exploring heterogeneity of treatment effects

Child-level variables that reflect subgroups	Groups	Alternative HYPOTHESIS	CRF AND REFERENCES
Child			
AGE	Subgroups: 5-11; 12-13	H1: Younger children will have better asthma control improvement from the interventions than older children.	
Sex	Male Female	H1: Sex will not affect improvement from the intervention. (dropped this Nov 2019)	
BASELINE ASTHMA CONTROL	Well-controlled Not well controlled	H1: patients with poor control at baseline will have more improved asthma control at 12 months as compared to patients who are well-controlled.	
ED visits (prior year at baseline)	0,1, 2 3+		
Inpatient visits (prior year at baseline)	0,1,2,3+		
Oral steroids COURSES IN PAST YEAR (at baseline)	0,1,2, 3-5, 6+	H1: patients with more than 3 prednisone in the previous year will have better response to the intervention for asthma control at 12 months.	
Home and caregivers			
HOUSEHOLD CHARACTERISTICS	 (1) Single Parent/Caregiver vs Multiple Caregivers (2) Rent vs. Own 		
Primary Caregiver- HIGHEST LEVEL achieved	Less than HS HS+ Graduate Level	H1: children of primary caregiver with less education will have poorer improvement asthma	

[These will be reduced to a small set of groups using latent class models.]

		control than those with more education	
Triggers at home			
TRIGGER EXPOSURES AT HOME	0 exposures 1, 2, 3+ exposures	H1: Children with 3+ asthma triggers in their bedroom at baseline will be less susceptible to improvement over time from the intervention.	
HOME OWNERSHIP STATUS	Own Rent	H1: There will be a difference in reduction of asthma triggers from the intervention by the status of home ownership	
Neighborhood and environment			
NEIGHBORHOOD CHARACTERISTICS	L & I violations Childhood Opportunity Index	H1: children who live in neighborhoods with higher L& I violations will have more symptoms and will improve less from the intervention. H2: children who live in neighborhoods with lower opportunities will have fewer reductions from the intervention of missed school days and symptoms	

6.1.2.1 Record linkage for patient's home address and ADI 12-digit FIPS code

Effective Spring 2020, CHOP EPIC system will geocode all patient's addresses into 12-digit FIPS codes. These codes will be downloaded from EPIC for each patient for the patient's address at the time of enrollment. Following changes in address will be too complex, and for that reason the address at the time of enrollment will be used. Record linkage with the ADI will proceed based on the 12-digit FIPS codes in EPIC and the ADI database.

Using this information, we will use the ADI index as a proxy for the neighborhood characteristics listed in Table 6.1b.

Patient utilization at baseline: Value in looking at by severity of exacerbation as the relevant outcome that is subject to modification. Whether to hospitalize a patient or to go to the emergency department are often judgment calls and therefore might be vary with the same level of exacerbation. Nevertheless, although baseline utilization might modify the effect of the intervention, the direction of that modification is uncertain. This analysis is therefore hypothesis generating.

We will reserve looking at outcomes until we have settled on candidate effect modifiers and using (or developing) indexes or summary measures.

We shall investigate treatment effect heterogeneity by using carefully pre-specified factors measured at baseline. Post baseline factors that might affect outcomes will fall under the topic of "mediation" (see below) and will be handled differently.

Because these key potential effect modifiers vary within the unit of randomization (school), these contrasts are essentially within-cluster comparisons with good statistical power (see below). Effect modification (moderation) can be estimated using the mixed effects and longitudinal models outlined previously without additional complexity. In all cases, effect modifiers (moderators) will be specified before the start of analysis to address concerns about multiple comparisons.

As of this writing, guidelines remain for publication on proper characterization of subgroups and the analysis of effects by subgroup. In brief, the following principles apply.

6.1.2.2 Estimating effect modification – scale dependency of interactions

Models for outcomes might be both additive (for asthma control) and multiplicative, as for use of log link generalized linear models. The contrasts of interest for permutation-test-based methods might also be additive (differences across the four treatment groups of differences in expected values over time).

Interaction (and effect modification) are scale dependent. A multiplicative model (log link) that has no interaction can give use to results that show effect modification on the additive scale. For that reason, we define "effect modification" to be on the additive scale for the key endpoints of change in asthma control scores and number of days of symptoms.

Estimation will follow the same principles and procedures as for the main analysis. Longitudinal data analysis models with splines for time will allow for estimation of expected values at time of randomization and at any time post randomization. For a single subgroup, the effect of the intervention (4 levels) can be compared by estimating eight expected values: four at time 0 and four at the endpoint time of interest. Contrasts across levels of the intervention and over time are estimated by subtraction.

6.1.3 Estimating confidence bounds for subgroups of interest

For ease in implementation and clarity of reporting, all confidence intervals will be estimated by bootstrap resampling (at the level of the school), stratified by school level treatment to maintain

constant the number of schools in each treatment category (eighteen). Resampling for longitudinal models will be done with 399 or 999 (if computational limits allow) samples to estimate percentile confidence bounds. (The 399th and 999th order statistics correspond to the 2.5th and 97.5th percentile bounds that form a 95% confidence interval). School level resampling will preserve the clustering and avoid overstating statistical significance.

For estimating confidence bounds to compare two subgroups will require a minimum of 16 expected values: four at time 0 and four at the endpoint time of interest for each of two subgroups.

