5.1.3 Patient-level analysis – marginal models

Second, marginal models using generalized estimating equations (Fitzmaurice 2011) will produce robust estimates that adjust for clustering at the school level. These methods tend to be robust for

non-continuous outcomes (non-identify link models) and those outcomes will likely apply to our outcomes of asthma control (possibly a log gamma model) and number of symptom days (possibly a log link Poisson or negative binomial model). In contrast to mixed effects models, marginal models do not rely on numerical integration. In addition to generalized estimating equations, quasi-least squares regression (Shults and Hilbe, 2014) will also be implemented. Quasi-least squares regression is an approach for estimation of the correlation parameters that is in the framework of generalized estimating equations; it allows for application of correlation structures that were previously unavailable for generalized estimating equations and can sometimes be implemented when generalized estimating equations fails to converge.

Marginal models tend to work poorly for designs with small numbers of clusters. In our case, the number of clusters (36) is relatively large. Nevertheless, we shall implement at least one method for adjusting for a number of clusters that is not large, as implemented in Stata's program xtgeebcv program (Gallis 2019) and R's program "saws" (Fay and Graubard 2001).

5.1.4 School-level analysis -- randomization-test-based methods.

Third, assumption-free, randomization-test-based (permutation test) methods that do not rely on assumptions of parametric models will also be applied. (Berger, 2000; Good, 2005; Small, 2008; Tang 2009; Rosenbaum 2002). (Also see Hayes and Moulton 2017)

We will use conventional levels of statistical significance (p=0.05) for all pre-specified comparisons for these aims. We shall not apply Bonferroni corrections for estimates from different modeling methods that use the same specification.

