6.1.5 Statistical software considerations

Methods for longitudinal analysis apply equally well to comparison of subgroups and to assess heterogeneity of treatment effects. Latent class analysis is available in SAS and more recently in Stata v15 et seq in "gsem", a program that will allow for different types of variables using to create latent classes. Python may also be used in sensitivity or primary analyses (Couronne, Vidailhet, Corvol et al. 2019).

6.1.6 Statistical Power for effect modification:

Owing to the absence of software for testing interaction effects, these estimates are based on our simulations conducted during the study design phase using Stata v 14.1. For a subgroup as small as 20% of the expected students (n=600) or 120 children, our design has 88% power to detect the effect of the navigator and 83% power to detect the effect of school for effect sizes of 0.5 for navigator, 0.6 for school, and a small interaction of 0.1.

This preliminary estimate does not anticipate issue of multiple comparisons. To the extent that the study reports differences in outcomes by baseline groups, simple Bonferroni corrections will apply.

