9.1 Multiple comparisons

Adjustments in critical levels for determining "statistical significance" when requested will follow these principles.

(a) If the contrast of interest is a primary or secondary outcome and pre-specified as such, we will make no adjustment

(b) All ad hoc, post SAP analyses and contrasts will be exploratory and hypothesis generating.

(c) All analyses for effect modification and mediation will consider the number of comparisons and make adjustments using simple Bonferroni correction for critical p-values.

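### SAP 6.1.3 gives the wrong order statistics for the 95% bootstrap percentile limits of subgroup effects; the stated 2.5/97.5 target is right and one sentence corrects it

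*SAP*

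**What the plan says.** SAP 6.1.3 says that confidence intervals for subgroups of interest will all come from bootstrap resampling of schools, stratified so that each school arm keeps its eighteen schools. On the number of resamples: "Resampling for longitudinal models will be done with 399 or 999 (if computational limits allow) samples to estimate percentile confidence bounds". The parenthesis that follows says: "The 399th and 999th order statistics correspond to the 2.5th and 97.5th percentile bounds", and presents these as the ends of a 95% interval. No other section of the SAP gives bootstrap ranks.

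On multiplicity, SAP 6.1.6 says: "To the extent that the study reports differences in outcomes by baseline groups, simple Bonferroni corrections will apply". SAP 9.1(c), on effect modification and mediation, says the analyses will "make adjustments using simple Bonferroni correction for critical p-values". Neither section states the number of comparisons, and neither says that the bootstrap intervals will be widened beyond 95%. Of the child-level factors in Table 6.1b, SAP 6.1.2 says: "These will be reduced to a small set of groups using latent class models".

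**The concern.** A percentile interval is defined by which ordered replicates are taken as its ends, so a rule that names the wrong ones does not give the interval it promises. Here each named order statistic has the same number as the planned count of resamples, which makes it the top replicate of that run. This is the SAP's only operational rule for subgroup intervals, and the SAP was finalised on 13 September 2022 as the governing document. A programmer who followed the parenthesis to the letter would not produce a 95% interval.

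The related question is whether 399 or 999 resamples are enough if the Bonferroni rule is carried over to these intervals. A percentile bound cannot lie beyond the most extreme replicate, so the number of resamples caps the number of comparisons that can be adjusted for.

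**Working it through.** **Inputs.** B = 399 or 999 resamples and limits at the 2.5th and 97.5th percentiles (SAP 6.1.3). Unadjusted two-sided level 0.05 (the level stated in SAP 5.1.4, and implied by the 2.5/97.5 limits). The number of comparisons, m, is not stated and is treated below as a range.

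**The SAP's own figure.** The percentile limit at probability p is the ordered replicate with rank k = (B + 1) × p.

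| B | rank for 2.5% | rank for 97.5% |
|---|---|---|
| 399 | 400 × 0.025 = 10 | 400 × 0.975 = 390 |
| 999 | 1000 × 0.025 = 25 | 1000 × 0.975 = 975 |

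The stated ranks, 399th and 999th, cannot be reproduced. The possible readings are:

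- B = 399: the 399th replicate is the maximum, at 399/400 = 99.75%. There is no 999th.
- B = 999: the 999th replicate is the maximum, at 999/1000 = 99.9%. The 399th is at 399/1000 = 39.9%.
- Each run's own named statistic: this gives an upper end only, and no lower limit.
- Both from the B = 999 run: the content is (999 − 399)/1000 = 60%.

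**Coverage.** In a simulation of 20,000 runs with a normal bootstrap distribution, coverage was 0.950 for the 10th to 390th of 399, 0.952 for the 25th to 975th of 999, and 0.605 for the literal pair from 999. Under the same normal assumption the expected maximum lies about 2.97 standard errors above the centre for 399 replicates and 3.24 for 999, against 1.96 for a 97.5% limit.

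**Bonferroni, if applied to the intervals.** The lower rank becomes k = (B + 1) × 0.05/(2m), and it must be at least 1. So m can be at most 0.05 × (B + 1)/2:

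- B = 399: 0.05 × 400/2 = 10
- B = 999: 0.05 × 1000/2 = 25

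| m | k at B = 399 | k at B = 999 |
|---|---|---|
| 2 | 5 | 12.5 |
| 5 | 2 | 5 |
| 10 | 1 | 2.5 |
| 11 | 0.909 (not available) | 2.273 |
| 25 | 0.4 (not available) | 1 |
| 26 | 0.385 (not available) | 0.962 (not available) |

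Two illustrations of m follow, both assumptions. Two latent classes, two marginal effects and the two endpoints named in SAP 6.1.2.2 give 1 × 2 × 2 = 4, which B = 399 can serve. Three classes compared pairwise give 3 × 2 × 2 = 12, which exceeds B = 399 but not B = 999.

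**Monte Carlo noise in one limit.** The standard deviation, in units of the standard error and for a normal bootstrap distribution, is about 0.14 for the 390th of 399. It is 0.38 for the 399th of 399 (m = 10) and 0.06 for the 9,975th of 9,999 (m = 10). These come from the exact distribution of the order statistic. The large-sample quantile formula gives only 0.32 for the second case and should not be used at the extreme replicate.

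**The case against.** The strongest reply is that the intention is clear and correct. The section asks for percentile bounds and names 2.5 and 97.5. Both 399 and 999 are sensible choices because (B + 1) × 0.025 is then a whole number, 10 or 25. The authors therefore very probably meant numbers of resamples and wrote order statistics. That is an inference, but a good one. The literal rule is also hard to follow by accident: it cannot be computed from 399 resamples, and from 999 it gives a visibly lopsided interval. This stands, and it limits the practical harm. It does not make the sentence right.

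A reader might also infer that 399 resamples cannot reach the Bonferroni level the SAP demands. The documents do not support that. The SAP states no number of comparisons, so there is no specific level to fail. It plans to collapse the child-level factors into a few latent classes, so counting every row of Table 6.1b for each intervention is not a fair basis for m. It also allows 999 resamples if computing permits. SAP 9.1(c) words the correction for critical p-values, not intervals, and SAP 6.1.2.1 says effect modification can be estimated with the mixed-effects and longitudinal models, which can supply p-values without bootstrap tails. What remains is a gap: the SAP does not say whether reported intervals will be adjusted, so an unadjusted 95% interval could exclude zero while the adjusted test is not significant.

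**Conclusion.** The parenthesis in SAP 6.1.3 is wrong as written. The ranks should be 10 and 390 of 399, or 25 and 975 of 999. Coded literally from 999 resamples, the interval has 60% content instead of 95%.

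It would go too far to conclude that the subgroup intervals will be wrong. That follows only from literal coding, and the stated percentile target points a careful programmer to the right ranks.

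The limits of 10 and 25 comparisons matter only if Bonferroni-adjusted bootstrap intervals are actually reported. They rest on a two-sided level of 0.05/m and plain percentile bounds. The coverage and noise figures also assume a normal bootstrap distribution.

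The point is confined to the Aim 2 subgroup intervals. The primary analysis does not use this rule. The SAP itself calls school-level effect modification exploratory and descriptive (6.1.1) and modification by baseline utilization hypothesis generating (6.1.2.1), and in 9.2 expects attempts to show heterogeneity to fail for lack of numbers. This is a minor correction.

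**What to change.** Replace the parenthesis in SAP 6.1.3 with: the 10th and 390th ordered replicates of 399, or the 25th and 975th of 999, give the 2.5th and 97.5th percentile limits. This costs one sentence and has no drawback.

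Add a sentence saying whether reported subgroup intervals stay at 95% or are Bonferroni-adjusted. If they are adjusted, fix m before outcomes are examined and choose B so that (B + 1) × 0.05/(2m) is a whole number well above 1. For example, m = 10 with B = 9,999 gives 10,000 × 0.05/20 = 25, so the limits are the 25th and 9,975th replicates. A smaller m needs fewer: m = 4 with B = 3,999 gives 4,000 × 0.05/8 = 25.

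The cost of adjustment is computing time. B = 9,999 is about 10 times the work of 999 and 25 times that of 399, and the SAP already mentions computational limits. If the intervals stay at 95%, the planned 399 or 999 resamples can remain, with a note that the adjusted test and the unadjusted interval may disagree and which of them governs.

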6.1.4 Data reduction through use of latent class methods

Each of the patient level factors can be combined into latent classes to arrive at a tractable number of levels for use in estimating heterogeneity of treatment effect. (Lanza 2013).

Examples appear in Zhang (2018) on defining subgroups with different clinical outcomes.

6.1.5 Statistical software considerations

Methods for longitudinal analysis apply equally well to comparison of subgroups and to assess heterogeneity of treatment effects. Latent class analysis is available in SAS and more recently in Stata v15 et seq in "gsem", a program that will allow for different types of variables using to create latent classes. Python may also be used in sensitivity or primary analyses (Couronne, Vidailhet, Corvol et al. 2019).

6.1.6 Statistical Power for effect modification:

Owing to the absence of software for testing interaction effects, these estimates are based on our simulations conducted during the study design phase using Stata v 14.1. For a subgroup as small as 20% of the expected students (n=600) or 120 children, our design has 88% power to detect the effect of the navigator and 83% power to detect the effect of school for effect sizes of 0.5 for navigator, 0.6 for school, and a small interaction of 0.1.

This preliminary estimate does not anticipate issue of multiple comparisons. To the extent that the study reports differences in outcomes by baseline groups, simple Bonferroni corrections will apply.

